- a) Dapagliflozin causes a rapid and significant reduction of EAT in type 2 diabetic patients
- b) Dapagliflozin-induced EAT reduction would be associated with a significant reduction of LV mass, independent cardiovascular risk factor.

ENDPOINTS:

Primary Endpoint: EAT (Epicardial fat thickness) will be measured with echocardiography according to the method described and validated by [name] et al. Full description of the measurement is reported in the section "Methodology"

Secondary Endpoint: LVM (left Ventricular Mass) will be measured with echocardiography according to the standard formula, fully described in the section "Methodology"

SPECIFIC OBJECTIVES

Primary Objective:

- a) Does treatment with Dapagliflozin cause a significant decrease in EAT in subjects with type 2 diabetes?

Secondary Objective:

- b) Does treatment with Dapagliflozin cause a significant decrease in LVM, through the reduction of EAT, in subjects with type 2 diabetes?

[figure not shown]
STUDY DESIGN

This will be an interventional, double-blind, parallel group, placebo controlled study in 100 overweight/obese type 2 diabetic subjects who are taking Metformin as monotherapy.

Individuals will be randomized in two groups of 50 patients, to receive additional Farxiga (Dapagliflozin) (F-group) or to remain on Metformin (M-group) plus placebo orally once daily.

[figure not shown]
- F-group: Dapagliflozin will be administered at the starting dose of 5 mg once daily, then if no safety issues will occur, it will be titrated up to 10mg once daily after 2 weeks. Metformin (from 500 mg twice daily to a maximum of 1000 mg twice daily) regimen will be continued to achieve fasting glucose between 80 and 140 mg/dl.
- M-group will be treated with Metformin plus placebo orally once daily for the duration of the study. Metformin (from 500 mg twice daily to a maximum of 1000 mg twice daily) regimen will be continued to achieve fasting glucose between 80 and 140 mg/dl.

Both groups will receive lifestyle and diabetes education, as part of the standard care.

STUDY TIMETABLE

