Participants will be scheduled for the first visit (visit 0) after an overnight fast. Patients will be randomly assigned to receive Farxiga 5 mg or placebo once daily. After 2 weeks patients will receive detailed instructions over the phone to titrate Farxiga or placebo up to 10 mg once daily. F- and M- group patients will undergo clinical examination, anthropometrics, transthoracic echocardiogram for EAT and LVM measurement and point of care (POCT) of fasting glucose and haemoglobinA1c (HbA1c) and estimated Glomerular Filtration Rate (eGFR) at each visit, baseline (visit t0), 3 (visit t3), and 6 months (visit t6)

STUDY POPULATION

Number of subjects to be studied: One hundred overweight/obese type 2 diabetic subjects.

Planned number of subjects to be screened: Five hundred subjects will be screened among the outpatient population who routinely refer to [name] of Miami Diabetes Clinic at the Diabetes Research Institute (UMMG-DRI), out-patient clinics. [name] visits approximately 2000 diabetic patients per year.

Anticipated number of trial sites: UMMG-DRI out-patient diabetes clinics, University of Miami.

INCLUSION CRITERIA

- Type 2 diabetes, as defined by ADA criteria
- HbA1c < 8% measured at least 1 week prior to the study
- BMI ≥ 27 kg/m²
- Pre-treatment with Metformin as monotherapy
- Age > 18 and < 65 years old
- Normal and stable hemodynamic status

EXCLUSION CRITERIA

- Known contra-indications to Farxiga, in accordance with risks and safety information included in the latest updated Prescribing Information
- Type 1 diabetes, as defined by American Diabetes Association (ADA) criteria
- Insulin dependent or treated type 2 diabetes
- Current use of other SGLT2 inhibitors, GLP- 1 analogs or DPP4 inhibitors
- Glomerular Filtration Rate (GFR) < 60 mL/min/1.73 m²
- Signs or symptoms of hypovolemia
- Patients with poor glycemic control (HbA1c ≥ 8%) will be excluded to maximize long-term patient retention without need
- History of diabetes ketoacidosis
- Patients with active bladder cancer or with a prior history of bladder cancer
- Acute or chronic infective, including genital mycotic infections
- Clinical signs or symptoms of New York Heart Association (NYHA) class III-IV heart failure
- Clinical or laboratory evidences of chronic active liver diseases
- Acute or chronic infective diseases
- Cancer or chemotherapy
- Current use of systemic corticosteroids or in the 3 months prior this study

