Reliability of echocardiographic measurement of EAT will be assessed by the intra-class correlation coefficient. Inter- and intra-observer reproducibility will be evaluated by the intra-class correlation coefficient in all subjects. Echocardiograms will be read by [name] and an experienced cardiac imaging technician who will be blinded to the patients' study group. Previously published studies have shown that intra- and inter-observer reproducibility of epicardial fat measurement was excellent. Intra-class correlation coefficients varied from 0.90 to 0.98 and from 0.93 to 0.98, respectively indicating good reproducibility and reliability. Both readers will be blinded to the subjects' clinical data. Although its advantages overcome the disadvantages, echocardiography measurement may have some limitations. Echocardiographic EAT is a linear measurement at a single location and therefore may not reflect the variability of fat thickness or total epicardial fat volume

Echocardiographic LVM and LVH measurement

LV mass will be estimated by using the anatomically validated formula of Devereux, and then adjusted as LV mass/body surface area (BSA) and LV mass/height^{2.7} (h^{2.7}). Left ventricular hypertrophy (LVH) will be defined as LV mass/BSA >134 g/m² for men and >110 g/m² for women and as LV mass/h^{2.7} >51 g/m^{2.7} in both sexes. Relative wall thickness (RWT) will be calculated as 2 posterior wall (PW)/LV end – diastolic – diameter. Four LV geometric patterns (normal, concentric remodeling, concentric hypertrophy, and eccentric hypertrophy) will be determined using values of RWT and LV mass as follows: normal (no LVH and RWT < 0.44), concentric remodeling (no LVH and RWT > 0.44), concentric hypertrophy (LVH and RWT > 0.44), and eccentric hypertrophy (LVH and RWT < 0.44).

Physical Examination

All anthropometric measures will be obtained by the study nurse. Height (in cm) and weight (in kg) will be measured, and BMI will be automatically calculated as weight in kilograms divided by the square of height in meters (kg/m²). Waist circumference (in cm) will be measured as the minimum circumference between the lower rib margin and the iliac crest. Hip circumference (in cm) will be measured as the widest diameter over the greater trochanters). Blood pressure will be measured in the seated position, using an automated cuff and digital readout, and entered by the study nurse into the electronic database.

Blood Measurements

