Fasting point of care tests will be obtained from all individuals according to the study design timetable. Blood parameters will be measured according to standard and previously described procedures.

Follow up of glucose profile Study patients will be advised to monitor their capillary glucose twice daily, fasting in the morning and post-prandially. Glucose profile will be tracked weekly by the research coordinator using myUhealth, a new and convenient UM online method of communication with the sponsor investigator, or by telephone. Research coordinator will inform the sponsor investigator on patients' glucose readings.

COMPLIANCE AND RETENTION STRATEGY We estimate that the majority of the participants who will be considered eligible will complete the study. Attrition can be estimated as lower than 10%. In the event that participants are lost to follow-up, the research coordinator will contact with the study participant by telephone. The research coordinator will be trained in effective telephone technique to maximize recruitment success.

STATISTICAL CONSIDERATIONS:

[name]' group previously showed and published that epicardial fat thickness decreased from 12.3 ± 1.8 to 8.3 ± 1 mm $P < 0.001$ after the 6-month very low calorie diet, accounting for a 32% reduction from the baseline. Average weight loss after the 6-month VLCD in those morbidly obese subjects was approximately 20 kg. It has been reported that Dapagliflozin can cause an approximately 1.5 kg decrease of body weight.

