We expect that Dapagliflozin will cause a significant decrease in EAT, but much smaller when compared to weight loss interventions such as a VLCD. EAT decrease has been shown to vary (between -12% and -32%) after different interventions. EAT reduction is anticipated to be between -15% and -25% after 3 months of treatment with Dapagliflozin. A hypothesis of at least 15% reduction in EAT is based on: a) the previously reported weight-loss caused by Dapagliflozin, b) previously-reported responsiveness (decrease) of EAT to pharmacological agents targeting the fat. A reduction of 15%, an absolute difference of 1.2 mm from baseline, will be considered not only statistically, but clinically significant of visceral fat reduction. It is worthwhile to note that a reduction of 0.4 and 1.4 mm in EAT after atorvastatin and bariatric surgery, respectively, was previously considered statistically and clinically significant. However, it is possible to expect a larger difference after 6 months of treatment

Given the reference value and the expected difference in EAT, the statistical power of the study (two-sided, $\alpha=0.05$) was calculated.

Outcome	Reference value \pm SD	Expected Difference	Detectable difference with 80% power $\alpha=0.05$	Detectable difference with >99% power $\alpha=0.05$
EAT (mm)	8 ± 3	-15-or -25%	-15% (absolute difference = 1.2)	-25% (absolute difference = 2)

A convenience sample of 50 individuals for each group will therefore provide the statistical power (80%) to detect an expected difference of -15% in the EAT before and after treatment with Dapagliflozin. Baseline SD of 3 is expected to lower to approximately 2 for the expected change. The expected change of SD will assure significant statistical power of the comparative test.

Study Hypothesis 1 Dapagliflozin causes a significant and rapid decrease in EAT. Comparative statistical analysis between F and M-group will be performed to tests this hypothesis. Continuous variables will be considered as age-adjusted and sex-adjusted means with their standard deviations (SDs). Two-tailed $p < 0.05$ indicates statistical significance. ANOVA model with adjustment for baseline will be used to calculate the changes (Δ) in EAT between baseline, 3 and 6 months in both F and M-group.

Study Hypothesis 2

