Dapagliflozin reduces LVM through an effect on EAT. Based on our previous data (36) we know that LVM reduction is independently related to epicardial fat reduction. We hypothesize that LVM will reduce in the F-group and better than in the M-group. ANOVA test with 95% CI will be used to calculate the changes (Δ) in study parameters between baseline, 3 and 6 months in both F and M-group. Relations between Δ epicardial fat, Δ BMI, Δ waist circumference and Δ LVM will be calculated using simple linear regression analysis. Variables with a $p < 0.1$ value on univariate analysis will be entered in different multivariate analysis models to assess the independent determinants of Δ LVM, as dependent variables. Echocardiographic epicardial fat will be compared to BMI, waist circumference and to waist-hip ratio as independent predictor of Δ LVM. The optimum sensitivity and specificity of threshold values of EAT to predict reduction in LVM will be examined by receiver operating characteristics (ROC) analysis by plotting sensitivity vs. 100 – specificity.

DATA HANDLING AND RECORD KEEPING:

Data Collection: Each of the dedicated clinic exam rooms at the UMMG-DRI provides direct access to the clinical research study electronic data capture (EDC) eVelos system provided by the Clinical Research Informatics and Data Management Unit of the Center for Health Informatics and Bioinformatics at UM. The sponsor investigator and research coordinator will collect and manage the data.

ETHICS:

Informed Consent

Eligible and willing participant will be contacted by the research coordinator and consented. Previous to the signing of the informed consent, extensive oral and written information will be given to the subjects, including information about risks associated with Dapagliflozin treatment (in accordance with the updated Prescribing Information) before initiating any study related activity.

Confidentiality of data The sponsor investigator will explain that participant confidentiality will be maintained, data will only be identified by a number and that their consent forms with identification number will be kept locked in a filing cabinet.

Protections against Risk

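### The EAT cut-off for predicting LVM reduction is chosen and assessed in the same patients without correction, so its reported sensitivity and specificity will be biased upward (minor)

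*Combined protocol and SAP*

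**What the plan says.** The analysis is one sentence at the end of Study Hypothesis 2, in Statistical Considerations: "The optimum sensitivity and specificity of threshold values of EAT to predict reduction in LVM will be examined by receiver operating characteristics (ROC) analysis". It adds only that sensitivity will be plotted against 100 minus specificity.

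The documents give no rule for what makes a threshold optimal. They give no hold-out or external sample, no cross-validation or bootstrap, no cut-off fixed beforehand, and no confidence interval for the ROC result. The data are those of the trial itself: "One hundred overweight/obese type 2 diabetic subjects" (Study Population), of whom "Individuals will be randomized in two groups of 50 patients" (Study Design). Attrition is put below 10% (Compliance and Retention Strategy), so about 90 or more should complete.

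Several inputs to the ROC are left open:

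- **Event.** It is described only by the words "to predict reduction in LVM", with no size.
- **LVM index.** Methodology provides LV mass, LV mass over body surface area and LV mass over height to the power 2.7. None is named for the ROC.
- **Visit.** Changes are to be analysed for "study parameters between baseline, 3 and 6 months in both F and M-group". The ROC sentence names no visit.
- **EAT variable and population.** The plan does not say whether EAT means the baseline value or the change, or whether one or both groups enter.

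**The concern.** An empirical ROC curve from about 100 patients is jagged. The point that looks best on it is partly the best by chance. Its sensitivity and specificity, read off the same curve, carry that chance advantage and will on average not be matched in new patients. This follows from the analysis as stated and does not depend on how well EAT tracks LVM.

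At stake is the credibility of any EAT threshold reported for LVM reduction. A reader would take its sensitivity and specificity as estimates of future performance. The open choices listed above add to the problem: if they are settled after the data are seen, the best-looking combination can be selected as well as the best-looking cut-off.

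**Working it through.** **The plan's own figure.** No figure is given for the ROC analysis. The only design calculation is 80% power for a 1.2 mm fall in EAT. It reproduces as a before/after comparison in 50 patients with SD 3: 3/√50 = 0.424; 1.2/0.424 = 2.83; 2.83 − 1.96 = 0.87; Φ(0.87) ≈ 0.81. It does not bear on this point.

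**Inputs from the documents.** 100 patients in total, 50 per group, attrition below 10%.

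**Inputs assumed because the documents do not give them.** The share with an LVM reduction, the strength of the EAT–LVM relation, the normal model, and the maximum Youden index, J = sensitivity + specificity − 1, as the meaning of optimum.

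**Step 1: what can truly be achieved.** With bivariate normal EAT and LVM change, correlation ρ and half counted as reducers, the best true cut-off is at the median, where J = (2/π)·arcsin(ρ).

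- ρ = 0: J = 0
- ρ = 0.2: (2/3.1416) × 0.2014 = 0.128
- ρ = 0.3: (2/3.1416) × 0.3047 = 0.194

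A cut-off estimated from data must on average do slightly worse than these ceilings.

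**Step 2: what the planned analysis would report.** 4,000 simulated trials per setting, with the cut-off chosen at maximum J. The apparent J is compared with the true J of that same cut-off.

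| Patients | ρ | Apparent J | True J |
|---|---|---|---|
| 100 | 0 | 0.12 | 0 |
| 100 | 0.2 | 0.22 | 0.11 |
| 100 | 0.3 | 0.28 | 0.17 |
| 90 | 0 / 0.2 / 0.3 | 0.12 / 0.22 / 0.28 | 0 / 0.11 / 0.17 |
| 50 (one arm) | 0 / 0.2 / 0.3 | 0.16 / 0.26 / 0.32 | 0 / 0.11 / 0.17 |

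The true values lie just below the Step 1 ceilings, as they should, and the apparent values lie well above them. At ρ = 0.2 the ratio of apparent to true is 0.22/0.11 = 2.0. At ρ = 0.3 it is 0.28/0.17 ≈ 1.6.

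**Step 3: a second model as a check.** A binormal marker with true AUC from 0.5 to 0.8 and 30% or 50% with a reduction. The overstatement, as the average of sensitivity and specificity, is:

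| Patients | Overstatement (percentage points) |
|---|---|
| 100 | 4.2–6.3 |
| 90 | 4.3–6.8 |
| 50 | 5.9–8.8 |
| 45 | 6.5–9.4 |

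Example: 100 patients, AUC 0.7, half with a reduction. Apparent sensitivity and specificity are 0.683 and 0.682, against true values of 0.630 and 0.639. J is then 0.365 against 0.269.

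**Step 4: the effect of the open choices.** This was an illustrative simulation with no association, 100 patients, two visits (assumed correlation 0.5 between them), two sizes of reduction and two EAT variables. Reporting the best result raised the mean apparent J from 0.12 to 0.22, with truth 0.

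**The case against.** The strongest reply is that little hangs on this. The ROC is one sentence about a supporting analysis of the secondary endpoint, and the plan says only that thresholds will be examined, not that one will be recommended. A worthless marker would not look convincing either. An apparent J of 0.12 is an average sensitivity and specificity of (1 + 0.12)/2 = 0.56, and even the 95th percentile of about 0.24 gives only 0.62. With no association, a test of the AUC against 0.5 rejects in about 5% of trials. The planned regression of LVM change on EAT change would also show the lack of a relation. All of this stands, and it keeps the severity low. It does not remove the bias when the relation is real but weak, where apparent accuracy is 1.6 to 2 times the truth. It is also true that the sizes rest on assumptions. The direction does not.

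A reader might infer three stronger points that the documents do not support.

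- **That any fall in LVM, however small, will count as a reduction.** The plan does not say so. It leaves the term undefined.
- **That counting any fall would itself inflate accuracy.** The effect runs the other way: measurement error in LVM change misclassifies patients and weakens the apparent relation. With a correlation of 0.5 between EAT and true LVM change, the AUC for any fall drops from 0.729 without error to 0.691 at reliability 0.7 and 0.643 at reliability 0.4.
- **That this ROC underpins the plan's claim for EAT as a clinical marker.** Significance and Innovation proposes EAT as a marker of visceral fat loss during treatment. An ROC of EAT against LVM neither supports nor refutes that.

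**Conclusion.** The point holds, at minor severity. Sensitivity and specificity at the selected EAT cut-off will be overstated because selection and assessment use the same patients and no correction is planned. Under the assumptions shown, the overstatement averages about 4 to 6 percentage points per measure with 100 patients, and about 6 to 9 with one arm of 45 to 50. On the Youden scale with 100 patients and half reducing LVM, it is about 0.10 to 0.12. Different prevalence, marker strength or selection rules would change the size but not the sign. That the definition of a reduction and the other ROC inputs are unset is a gap that leaves room for choice after the data are seen; it is not evidence of any particular rule. The primary EAT comparison and the between-group LVM comparison are not affected.

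**What to change.** Amend the ROC sentence in Study Hypothesis 2 as follows.

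1. **Main result.** Report the AUC with a 95% CI. It needs no cut-off, so it does not carry the cut-off selection bias.
2. **Cut-off accuracy.** Report sensitivity and specificity at a selected cut-off only after bootstrap optimism correction, with the cut-off search repeated in every resample. In a simulation under the Step 2 assumptions this removed most of the bias. Cross-validation or an independent sample would also serve.
3. **Label.** Call the cut-off exploratory.
4. **Set before the data are seen.** State the EAT variable (baseline or change), the LVM index, the visit, the population (one or both groups), the rule for choosing the cut-off, and what counts as a reduction in LVM. The documents give reliability figures for EAT only. A definition of reduction based on LVM measurement error would therefore need a figure obtained elsewhere, with its source stated.

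The cost is a few sentences and a few lines of code, with no new patients or measurements. The downside is that the reported accuracy will look lower.

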Dapagliflozin is a new and emerging anti-diabetes medication. Dapagliflozin is a selective sodium-glucose cotransporter 2 (SGLT2) inhibitor, reduces hyperglycemia in patients with type 2 diabetes mellitus (T2DM) by increasing urinary glucose excretion, and weight loss is a consistent associated finding. Because dapagliflozin increases urinary glucose excretion, weight loss could result from reduced body fat secondary to caloric loss or from fluid loss secondary to osmotic diuresis or from a combination of both factors. Nevertheless, whether Dapagliflozin may cause a reduction in visceral fat is unknown. Also whether Dapagliflozin can reduce EAT, visceral fat of the heart, and improve cardiac performance, is unexplored.

Hence, in this study we would like to test the hypotheses that Dapagliflozin (a) causes a rapid and significant reduction of EAT, as marker of visceral fat, in type 2 diabetic patients, (b) Dapagliflozin-induced EAT reduction is associated with a significant reduction of LVM. These hypotheses would be tested in an interventional, double-blind, parallel group, placebo controlled study in 100 overweight or obese type 2 diabetes subjects.

This proposal therefore contains a number of novel concepts and an innovative methodology with immediate and important clinical application.

Key words: visceral fat; epicardial fat; Dapagliflozin; type 2 diabetes

Background

Visceral Fat and Cardiovascular Risk

[figure not shown]
Different body fat distribution has been clearly associated with different cardiovascular risk. A number of evidences indicate that subjects with excess visceral fat accumulation are at higher risk for cardio-metabolic diseases and diabetes. Traditionally, most of the attention has been focused to the intra-abdominal visceral fat accumulation and waist circumference has been largely used as surrogate marker of visceral adiposity. However, waist circumference may provide incomplete information or be subject to operator variability. Imaging studies, as well as MRI or computed tomography are certainly more accurate estimates of body visceral fat content, but more costly and invasive. With this in mind, I have focused my attention to an emerging visceral fat depot, the epicardial fat, and developed a methodology through which epicardial fat can be visualized and measured using standard two-dimensional echocardiography with several advantages, including its low cost, easy accessibility and good reproducibility

Epicardial Fat

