- Known or suspected allergy to Dapagliflozin, excipients, or related products
- Pregnant, breast-feeding or the intention of becoming pregnant
- Females of childbearing potential who are not using adequate contraceptive methods

Withdrawal Criteria

Study subject may withdraw at will at any time.

Repeated eGFR <60 mL/min/1.73 m² and hypoglycaemic (< 70 mg/dl) episodes will mandate discontinuation of the patient from the study.

VISIT PROCEDURES

Once patient eligibility and written consent are obtained, the participant is then scheduled for the baseline (t0) clinic visit through the University of Miami UChart (Epic) electronic system. The visits will be coordinated by the research coordinator. Each patient will undergo a baseline echocardiographic study for the measurement of EAT and LVM. Each patient will also have a full physical examination, body weight, height, waist and hip circumference measured, a point of care of fasting glucose and haemoglobinA1c (HbA1c). Echocardiographic study will be performed on site by [name] and by an experienced cardiac imaging technician who will be trained to measure echocardiographic EAT by [name]. The same visit procedures will be repeated after 3 (t3) and 6 (t6) months.

DESCRIPTION OF STUDY SITE

UM Miller School of Medicine has been the site of several National Institutes of Health studies and many peer-reviewed, epidemiologic and health services research publication. The Division of EDM is fully equipped and trained to visit, follow up and manage patients with diabetes. UMMG-DRI is fully accredited and equipped to perform state-of-the-art diagnostic tests assisting in the diagnosis and management of diabetes. The Division is also equipped with a state-of-the-art echocardiographic unit, Siemens, Acuson, USA, for the measurement of the EAT. [name] pioneered the echocardiographic measurement of the epicardial fat and he is considered the leading expert in epicardial fat research

METHODOLOGY

Informed consent will be in place before any study related procedures will be conducted.

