Echocardiographic Epicardial Fat Thickness Echocardiographic studies will be performed onsite by [name] and a technician trained in echocardiography. Standard parasternal and apical views will be obtained in the left lateral decubitus position. All echocardiograms will be recorded on DVDs and subsequently digitized will be analyzed offline for epicardial fat thickness quantification according to the method firstly described and validated by [name] et al (9-10). Briefly, epicardial fat will be identified as the echo-free space between the outer wall of the myocardium and the visceral layer of pericardium. Epicardial fat thickness will be measured perpendicularly on the free wall of the right ventricle at end-systole in three cardiac cycles. Parasternal long- and short-axis views allow the most accurate measurement of epicardial adipose tissue on the right ventricle, with optimal cursor beam orientation in each view. Maximum epicardial fat thickness will be measured at the point on the free wall of the right ventricle along the midline of the ultrasound beam, perpendicular to the aortic annulus, used as anatomical landmark for this view. For the midventricular parasternal short-axis assessment, maximum epicardial fat thickness will be measured on the right ventricular free wall along the midline of the ultrasound beam, perpendicular to the interventricular septum at mid-chordal and tip of the papillary muscles level, as anatomic landmark. The average value of three cardiac cycles from each echocardiographic view will be considered.

Reliability of echocardiographic measurement of EAT

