The risks to patients are extremely minimal in this study. There is a theoretical small increased risk of hypoglycaemic events in the Dapagliflozin + metformin group. There are no other foreseen risks to participants involved in the study. Patients will be required to remove their shirts for echocardiographic evaluation and may feel embarrassed. In addition, the patient may worry that their participation might be disclosed in a weight loss program. Patients will be informed of the echocardiography procedure prior to consenting. There may be some embarrassment from having their waist and hips measured three times throughout the course of a year. Participants

would undergo blood test regardless their participation in the study. The researcher assistant will be advised of any required sensitivity towards participating members

Other Ethical considerations

The study has been submitted to the University of Miami local institutional review board (IRB). Final approval is pending, but highly anticipated. The study will be conducted in accordance with the Declaration of Helsinki. The study will be conducted in accordance with the ICH GCP guidelines. The sponsor-investigator will comply with all applicable regulatory and legal requirements, ICH GCP guidelines and the Declaration of Helsinki in obtaining and documenting the informed consent.

STUDY SCHEDULE:

Planned recruitment period: 1 year

Expected milestones:

- start of study: 01/01/2015
- first patient first visit 01/01/2015
- last patient last visit 12/01/2016
- Planned completion of integrated final study report 01/1/2017

STUDY DRUGS AND MATERIALS:

Study medication

FARXIGA (Dapagliflozin) is SGLT2 inhibitor indicated as an adjunct to diet and exercise to improve glycemic control in adults with type 2 diabetes mellitus

Study Medication supply

Farxiga will be supplied to each study subjects by Astra Zeneca

Labelling of Study Medication

No IND is required. Study medication will be in accordance to current labelling.

Storage and Drug Accountability of Study Medication

The sponsor-investigator will ensure the availability of proper storage conditions and record and evaluate the temperature.

Randomization

This will be an open randomized study. The method of allocation generation will be a computerized random-number generator. The sequence will be generated by the process of restricted randomization. This has greater potential benefit in small trials, as in the present study.

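### The Randomization text calls the trial open, while the summary and STUDY DESIGN call it double-blind and placebo controlled, and nothing says which prevails

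*Combined protocol and SAP*

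**What the plan says.** **Blinding status.** The introductory summary says the hypotheses will be "tested in an interventional, double-blind, parallel group, placebo controlled study in 100 overweight or obese type 2 diabetes subjects". STUDY DESIGN repeats this: "This will be an interventional, double-blind, parallel group, placebo controlled study in 100 overweight/obese type 2 diabetic subjects". The Randomization text says: "This will be an open randomized study".

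**Control treatment.** STUDY DESIGN states: "M-group will be treated with Metformin plus placebo orally once daily for the duration of the study". STUDY TIMETABLE adds that after two weeks "patients will receive detailed instructions over the phone to titrate Farxiga or placebo up to 10 mg once daily".

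**Measurement of the primary endpoint.** Under VISIT PROCEDURES, scans are done on site by a named operator and "by an experienced cardiac imaging technician who will be trained to measure echocardiographic EAT". METHODOLOGY says: "All echocardiograms will be recorded on DVDs and subsequently digitized will be analyzed offline". The section on reliability of the EAT measurement has the recordings read by a named reader and "an experienced cardiac imaging technician who will be blinded to the" patients' study group. A later sentence there masks both readers, but mentions only clinical data.

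**Supply, labelling and code breaking.** The supply text names Farxiga and no placebo. The labelling text refers only to the current label. The code-break text under REPORTING OF SERIOUS ADVERSE EVENTS is conditional: it says what happens in blinded trials, not whether this trial is one.

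**The concern.** A trial cannot be both open and double-blind. Staff who randomize and dispense from the STUDY DRUGS AND MATERIALS section would run one trial; staff who work from STUDY DESIGN would run another.

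The choice matters because EAT is measured by an operator on a scale of millimetres: the reference value is 8 mm and the difference sought is 1.2 mm. Knowledge of the arm could affect how images are acquired. It could also affect what patients do, in a trial where both groups receive lifestyle education. A report that called the trial double-blind would contradict its own Randomization section.

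**Working it through.** No sample size, power or alpha figure in the plan depends on blinding status, so there is nothing to reproduce. The check is a comparison of every statement that bears on blinding.

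**Step 1: direct statements.** Two places say double-blind (introductory summary, STUDY DESIGN). One says open (Randomization). All three describe the whole trial.

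**Step 2: can *open* be read narrowly?** Nothing limits the word to a phase, a role or the way the allocation sequence is produced. The sentences that follow it describe a computer-generated, restricted sequence, which is compatible with either status.

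**Step 3: indirect text pointing to double-blind.** The control group takes a placebo daily throughout, and the placebo is stepped up alongside the active drug. This establishes placebo control and makes masking the natural reading. STUDY TIMETABLE does not itself mention blinding.

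**Step 4: indirect text pointing the other way.** The supply and labelling text describes neither a placebo nor blinded labels. The Randomization text names no concealment procedure and no holder of the code. The double-blind version therefore has no operational support in the section where it would be expected.

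**Step 5: does anything settle it?** The code-break text is conditional and does not. Blinded echocardiogram reading does not either, since it is compatible with both an open and a masked trial.

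**Step 6: what each status would leave masked.** The plan does not list roles, so the middle column takes double-blind in its usual sense.

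| Role | If double-blind | If open |
|---|---|---|
| Patients | masked | know their arm |
| Treating staff | masked | know the arm |
| Those acquiring images | masked | no text protects acquisition |
| Readers of the recordings | masked | study-group masking stated for the technician, and for both readers if the clause is read broadly; analysis is offline |

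The last cell depends on whether the clause about being blinded to study group attaches to both readers or only to the technician. The grammar allows either.

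**Step 7: size.** The documents give no estimate of a shift in EAT related to knowing the arm. The intra-class correlations of 0.90 to 0.98 describe agreement between readings. They neither measure nor exclude a shift between arms.

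**The case against.** **The word may be a leftover.** Two design statements, the placebo regimen and the parallel titration all fit a double-blind trial. That is the likelier intent, but it is an inference: the supply and labelling text does not bear it out, and no sentence overrides the Randomization text.

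**Blinded reading protects the endpoint.** This stands in part. Masked reading and offline analysis would survive an open design. They do not reach image acquisition or patient behaviour.

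Three stronger conclusions are tempting, and the documents do not support them.

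- *That under the Randomization text nobody would be masked.* The Randomization text does not cancel the reading provisions. Together they describe an open trial with masked endpoint reading.
- *That a masked reader would meet patients who know their arm.* The scanning technician and the reading technician carry the same role title, but the plan does not say they are one person, nor that the technician would learn the arm.
- *That the false-positive rate would rise to a particular figure.* With SD of change 2 mm and 50 per arm, SE = 2 × √(2/50) = 0.40 mm. Then P(reject) = P(Z > 1.96 − d/SE) + P(Z < −1.96 − d/SE), where d is a shift between arms with no true effect. For d of 0.1, 0.2 and 0.4 mm this gives 5.7%, 7.9% and 17.0%. With SD 3 mm (SE 0.60 mm) it gives 5.3%, 6.3% and 10.2%. The arithmetic is right, but every d is assumed, the SD of 2 mm rests on an ambiguous sentence in STATISTICAL CONSIDERATIONS, and the SE ignores the planned baseline adjustment. If the trial is run double-blind, no such shift is expected. These figures are not evidence about this trial.

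**Conclusion.** Wrong as written. The contradiction is explicit, concerns a defining design feature and cannot be resolved from the visible text. Confidence in that is high, and the case for correction rests on the contradiction alone.

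The consequence is bounded. On the literal open reading, patients, treating staff and image acquisition are unmasked, while reading of the recordings is at least partly protected. The effect on the EAT comparison may be nil or material; the documents do not allow it to be sized.

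One limit applies: the opening page and the two figures by STUDY DESIGN were not available for this check, so the absence of a precedence statement is established for the remaining text only.

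**What to change.** State one blinding status throughout.

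- **If double-blind** (favoured by the placebo text): in the Randomization sentence, replace *open* with *double-blind, placebo-controlled*. Extend the supply and labelling text to a matching placebo with blinded labels. Confirm that the code-break text under REPORTING OF SERIOUS ADVERSE EVENTS applies to this trial.
- **If open:** remove the double-blind label from the introductory summary and STUDY DESIGN. Reconcile the placebo wording there and in STUDY TIMETABLE with what patients are actually given. Limit the claim to blinded endpoint reading.
- **In either case:** reword the reliability section along the lines of *each of the two readers is masked to study group as well as to clinical data*.

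The cost is a few text edits, with no extra patients or visits. The double-blind route adds a supply cost if matching placebo has not been arranged; the open route gives up the double-blind claim. Coding the recordings before reading, randomizing the reading order and removing visit dates are possible refinements, but none is needed to remove the contradiction.
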